3. DESCRIPTION OF DESIGN AND TRIAL POPULATION

3.1 OVERALL TRIAL DESIGN AND PLAN

This single-rising dose trial is designed as single-blind, partially randomised, and placebo-controlled within parallel dose groups. “Partially” means that randomisation is done only in the second half of subjects of each dose level. For safety reasons the first half of subjects within each dose group will be administered study drug in a fixed sequence which is unknown to the volunteers: first subject active, second placebo, third active, fourth active.

A total of 48 healthy male subjects is planned to participate in the trial, according to 6 sequential groups comprising 8 subjects per group. However, additional subjects may be entered to allow testing of intermediate doses within the planned dose range on the basis of experience gained during trial conduct (e.g. preliminary PK data), i.e. the actual number of subjects entered may exceed 48. Such changes may be implemented via non-substantial CTP Amendments.

Within each dose group, 6 subjects will receive the active drug and 2 will receive placebo. Only one dose is tested within each dose group. Each dose group will consist of 3 cohorts which will be treated subsequently for safety reasons (see also [Section 2.3](#)).

The dose groups to be evaluated are outlined in [Table 3.1: 1](#) below.

Table 3.1: 1 Dose groups

Dose Group	1	2	3	4	5	6
Dose (mg)						
Number of subjects	8	8	8	8	8	8
Subjects receiving placebo	2	2	2	2	2	2
Subjects receiving active drug	6	6	6	6	6	6
Subject numbers						
Replacement numbers						

The dose groups will be investigated consecutively in ascending order of doses, maintaining a time interval of at least 21 days between the first drug administration in the previous dose group and treatment of a subject in the subsequent dose group. The decision to proceed to the next dose group will be based upon the safety and tolerability data of the preceding dose groups. The next dose will only be given if, in the opinion of the investigator, no safety concerns arose in the preceding dose group (i.e. no dose-limiting events occurred) and if none of the pre-specified trial-specific stopping criteria were met (refer to [Section 3.3.4.2](#)).

A documented Safety Review must take place prior to each dose escalation, but not earlier than 7 days after administration of last subject of a given dose level. Furthermore, an unscheduled safety review meeting can be requested anytime for any reasonable cause by the

Principal Investigator (or an authorised deputy) or the sponsor of the study, e.g. because of any unforeseen adverse events, etc. Dose escalation will only be permitted if no safety concerns exist in the opinion of the Principal Investigator (or an authorised deputy) and the Trial Clinical Monitor (or an authorised deputy).

The minimum data set for review consists of the following data (for the current dose group, safety data of at least 6 subjects having completed Day 8 will be required):

- AEs in the current and preceding dose groups (including clinically relevant findings from ancillary safety testing listed below) (Note: AEs may be ongoing at the time of Safety Reviews and AE information may be subject to change prior to Database Lock)
- Results from 12-lead EGG and continuous ECG monitoring in the current and preceding dose groups.
- Vital signs in the current and preceding dose groups
- Clinical laboratory tests in the current and preceding dose groups
- Preliminary PK/PD data for selected dose groups and time points as per [Section 7.3.4](#)
- Check of criteria for stopping subject treatment as per [Section 3.3.4.1](#)

The decision to escalate the dose will be made jointly by the Principal Investigator (or an authorised deputy) and the Trial Clinical Monitor (or an authorised deputy) after in-depth analysis of all available safety data, especially SAEs (if occurred), AEs and out-of-range laboratory results (if considered clinically significant).

Safety Reviews can be conducted face-to-face or by video/telephone conference. The investigator or project management team at the clinical site will be responsible for organization and minutes of the review meetings. Safety data will be provided and presented by the Principal Investigator (or an authorised deputy). Preliminary PK/PD will be provided by the sponsor as per [Section 7.3.4](#). Minutes will be signed off by the Principal Investigator (or an authorised deputy) and the Trial Clinical Monitor (or an authorised deputy) and filed in the ISF and TMF.

The investigator (after consultation with the sponsor) is allowed to alter the scheduled dose levels (e.g. add an intermediate dose level) within the planned dose range on the basis of experience gained during the study. In this case, the total number of subjects in this trial might increase. The investigator and/or the sponsor should stop dose escalation in case the safety evaluation leads to concerns that would not allow higher dosing.

An overview of all relevant trial activities is provided in the [Flow Chart](#). For visit schedules and details of trial procedures at selected visits, refer to [Sections 6.1](#) and [6.2](#), respectively.

3.1.1 Administrative structure of the trial

The trial will be conducted at the Clinical Pharmacology Unit (CPU) of _____, under the supervision of the Principal Investigator.

The trial medication will be provided by the Clinical Trial Supplies Unit (CTSU), BI Pharma GmbH & Co. KG, Biberach, Germany.

On-site monitoring will be performed by BI or a contract research organisation appointed by BI.

Safety laboratory tests will be performed by local laboratories of the trial site (e.g.).

The analyses of BI 655088 concentrations in plasma will be performed by the Department of Drug Metabolism and Pharmacokinetics, Boehringer Ingelheim, Ridgefield, USA.

The analyses of ADA will be performed in the Bioanalytical Laboratories of ,

The analyses of exploratory biomarkers in blood will be performed at the Department of TMCP/TMBT, BI Pharma GmbH & Co. KG, Biberach, Germany.

The digitally recorded 12-lead ECGs may be sent to a specialised contract research organisation (e.g.) for additional central evaluation.

The trial is sponsored by Boehringer Ingelheim Pharma GmbH & Co. KG, Germany.

3.2 DISCUSSION OF TRIAL DESIGN, INCLUDING THE CHOICE OF CONTROL GROUP

For single-rising dose trials, the design described in [Section 3.1](#) is viewed favourable under the provision not to expose the subjects involved to undue risks since the main study objective is to investigate safety and tolerability of BI 655088.

With the rising dose design, single-blind conditions regarding the subject's treatment (active or placebo) are maintained within each dose group. However, the current dose level will be known to subjects. The disadvantage of this trial design is a possible observer bias with regard to the dose-depending effects as well as time effects, but it has the virtue of minimizing subject risk by sequentially studying ascending doses. As time-effects are expected to be small relative to the differences between the doses in the broad range investigated, unbiased comparisons between treatments can still be expected.

The single-blind conditions may introduce additional observer bias, e.g. when assessing AEs in this first-in human trial. Thus every effort will be made to enhance the objectivity of investigator's observations. The same applies especially to the second subject of each dose level who is administered placebo treatment by defined study procedure.

It is standard in trials involving healthy volunteers to include a placebo group as control for the evaluation of safety, tolerability and pharmacodynamic effects. Each dose group consists of 8 subjects with 6 on active treatment, and 2 on placebo. The placebo control group includes all subjects of all dose groups treated with placebo. 6 subjects per active treatment group are in general considered as sufficient for exploratory evaluations.

3.3 SELECTION OF TRIAL POPULATION

It is planned that 48 healthy male will enter the study. The actual number of subjects entered may exceed the total of 48 if additional intermediate doses will be tested (see [Section 3.1](#)). Subjects will be recruited from the volunteers' pool of the trial site.

Only male subjects will be included into the study because hitherto no data on reproductive toxicology are available.

A log of all subjects enrolled into the study (i.e. having given informed consent) will be maintained in the ISF at the investigational site irrespective of whether they have been treated with investigational drug or not.

3.3.1 Main diagnosis for study entry

The study will be performed in healthy subjects.

3.3.2 Inclusion criteria

Subjects will only be included into the trial, if they meet the following criteria:

1. Healthy male subjects according to the investigator's assessment, based on a complete medical history including a physical examination, vital signs (BP, PR), 12-lead ECG, and clinical laboratory tests
2. Age of 18 to 50 years (incl.)
3. BMI of 18.5 to 29.9 kg/m² (incl.)
4. Signed and dated written informed consent prior to admission to the study in accordance with GCP and local legislation

3.3.3 Exclusion criteria

Subjects will not be allowed to participate if any of the following general criteria apply:

1. Any finding in the medical examination (including BP, PR or ECG) is deviating from normal and judged as clinically relevant by the investigator
2. Repeated measurement of systolic blood pressure outside the range of 90 to 140 mmHg, diastolic blood pressure outside the range of 50 to 90 mmHg, or pulse rate outside the range of 45 to 90 bpm
3. Any laboratory value outside the reference range that the investigator considers to be of clinical relevance
4. Any evidence of a concomitant disease judged as clinically relevant by the investigator
5. Gastrointestinal, hepatic, renal, respiratory, cardiovascular, metabolic, immunological or hormonal disorders
6. Diseases of the central nervous system (including but not limited to any kind of seizures or stroke), migraine, and other relevant neurological or psychiatric disorders
7. History of relevant orthostatic hypotension, fainting spells, or blackouts
8. Chronic or relevant acute infections

9. History of relevant allergy or hypersensitivity (including allergy to the trial medication or its excipients)
10. Use of drugs (including any biological agent) with a long half-life (more than 24 h) within 30 days or less than 10 half-lives of the respective drug (whichever is greater) prior to administration of trial medication
11. Within 10 days prior to administration of trial medication, use of drugs that might reasonably influence the results of the trial or that might prolong the QT/QTc interval
12. Participation in another trial where an investigational drug has been administered within 60 days or 10 half-lives (whichever is greater) prior to planned administration of trial medication
13. Smoker
14. Ex-smoker who has stopped smoking less than one year prior to enrolment and/or who has a history of equal or more than 10 pack years
15. Alcohol abuse (consumption of more 30 g per day)
16. Drug abuse or positive drug screening
17. Blood donation of more than 100 mL within 30 days prior to administration of trial medication or intended donation during the trial
18. Intention to perform excessive physical activities within one week prior to administration of trial medication or during the trial
19. Inability to comply with dietary regimen of trial site
20. A marked baseline prolongation of QT/QTc interval (such as QTc intervals that are repeatedly greater than 450 ms) or any other relevant ECG finding at screening
21. A history of additional risk factors for Torsades de Pointes (such as heart failure, hypokalemia, or family history of Long QT Syndrome)
22. Subject is assessed as unsuitable for inclusion by the investigator, for instance, because considered not able to understand and comply with study requirements, or has a condition that would not allow safe participation in the study

23. History of tuberculosis infection and/or a confirmed positive Quantiferon TB-Gold test
24. Subjects who in the investigator's judgement are perceived as having an excessive risk of thromboembolism (TE) for example because of a personal history and/or a first degree relative with a personal history with onset under the age of 55 of significant TE, including but not limited to deep vein thrombosis, pulmonary embolism, cortical sinus thrombosis, coronary and cerebrovascular events, cardiovascular disease, and peripheral arterial insufficiency
25. Abnormal results of coagulation values indicating an increased risk for bleeding or thromboembolism or complicating the safety evaluation during the study as determined by the investigator.
26. Deficiency of antithrombin III or protein S or protein C
27. Clinically relevant abnormal result of oral glucose tolerance test at baseline
28. Estimated glomerular filtration rate (eGFR) according to CKD-EPI formula < 90 mL/ min at screening ([R12-1392](#))

29. Urinary albumin/creatinine ratio (UACR) \geq 30 mg albumin / g creatinine at screening

For study restrictions, refer to [Section 4.2.2](#).

3.3.4 Removal of subjects from therapy or assessments

3.3.4.1 Removal of individual subjects

An individual subject is to be removed from the trial if:

1. The subject withdraws consent, without the need to justify the decision
2. The subject needs to take concomitant drugs that interfere with the investigational product or other trial medication
3. The subject is no longer able to participate for other medical reasons (such as surgery, adverse events, or diseases)
4. An AE or clinically significant laboratory change or abnormality occurred that the investigator judges to warrant discontinuation of treatment. This may include cases of sustained symptomatic hypotension (BP $<$ 90/50 mmHg) or hypertension (BP $>$ 180/100 mmHg) or of clinically relevant changes in ECG requiring intervention as well as unexplained liver enzyme elevations at any time during the trial.
5. The subject shows an elevation of AST and/or ALT \geq 3-fold ULN combined with an elevation of total bilirubin \geq 2-fold ULN (measured in the same blood sample) and/or needs to be followed up according to the 'DILI checklist' provided in the ISF.

In addition to these criteria, the physician may discontinue subjects at any time based on his or her clinical judgment.

A subject can also be removed from the trial if eligibility criteria are being violated or if the subject fails to comply with the protocol (for instance, by non-adherence to dietary rules, or non-attendance at study assessments).

If a subject is removed from or withdraws from the trial prior to the administration of trial medication, the data of this subject will not be entered in the case report form (CRF) or trial database and will not be reported in the clinical trial report (CTR). If a subject is removed from or withdraws from the trial after administration of trial medication, this will be documented and the reason for discontinuation must be recorded in the CRF. In this case, the data will be included in the CRF/trial database and will be reported in the CTR. At the time of discontinuation a complete end of trial examination will be performed if possible and the information will be recorded in the CRFs. These discontinuations will be discussed in the CTR.

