5.2.2.2 Adverse event collection and reporting

AEs collection

[figure not shown]
Upon enrolment into a trial, the subject's baseline condition is assessed (for instance, by documentation of medical history/concomitant diagnoses), and relevant changes from baseline are noted subsequently.

Subjects will be required to report spontaneously any AEs as well as the time of onset, end, and intensity of these events. In addition, each subject will be regularly assessed by the medical staff throughout the clinical trial and whenever the investigator deems necessary. As a minimum, subjects will be questioned for AEs (and concomitant therapies) at the time points indicated in the [Flow Chart](#). Assessment will be made using non-specific questions such as 'How do you feel?'. Specific questions will be asked wherever necessary in order to more precisely describe an AE.

A careful written record of all AEs shall be kept by the investigator in charge of the trial. Records of AEs shall include data on the time of onset, end time, and intensity of the event as well as any treatment or action required for the event and its outcome.

The following must be collected and documented on the appropriate CRF(s) by the investigator:

- From signing the informed consent onwards through the residual effect period (REP), until individual subject's end of trial:
 - All AEs (serious and non-serious) and all AESIs.
 - The only exception to this rule are AEs (serious and non-serious) and AESIs in Phase I trials in healthy volunteers, when subjects discontinue from the trial due to screening failures prior to administration of any trial medication. In these cases, the subjects' data must be collected at trial site but will not be entered in the CRF or trial database and will not be reported in the CTR.
- After the individual subject's end of trial:
 - The investigator does not need to actively monitor the subject for AEs but should only report relevant SAEs and relevant AESIs of which he may become aware of.

The residual effect period (REP) for BI 655088, when measurable drug levels or PD effects are still likely to be present, is not known for this first-in-human trial. Therefore all AEs reported until the end of trial examination will be considered on treatment; please see [Section 7.3.3](#). Events which occurred after the end of trial examination will be considered as post treatment events.

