5.2.3.1 Oral glucose tolerance test (oGTT)

An oGTT will be performed on the morning of Day -5 to -1 (baseline) and Day 29. After blood drawing for determination of fasting plasma glucose and serum insulin, 75 g of glucose will be dissolved in 200 mL water and swallowed by the subject. Thirty minutes, 1, 2 and 3 hours after intake of the glucose solution, further blood samples will be taken for glucose and insulin measurement. Blood samples for glucose measurements will be drawn in a 2 mL sodium fluoride (NaF) tube. Blood samples for insulin measurements will be drawn in a 2.5 mL serum tube.

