6. INVESTIGATIONAL PLAN

6.1 VISIT SCHEDULE

Exact times of measurements outside the permitted time windows will be documented. The acceptable time windows for screening and end of trial examination are given in the [Flow Chart](#).

Oral glucose tolerance test at baseline may be done within 8 days prior to the drug administration, i.e. the acceptable deviation from Day -5 will be -3 days.

Study measurements and assessments scheduled to occur 'before' trial medication administration on Day 1 are to be performed and completed within a 3 h-period prior to the start of trial drug administration (including blank values for PK and biomarkers).

The acceptable deviation from the scheduled time for vital signs (BP, PR, and body temperature) and ECG will be:

- ± 15 min up to including 12 h
- ± 30 min from after 12h up to including 48 h

The acceptable deviation from the scheduled time for laboratory samples and bleeding time:

- ± 5 min up to including 2 h
- ± 15 min from after 2h up to including 12 h
- ± 30 min from after 12h up to including 48 h
- ± 120 min from after 48 h up to Day 8
- ± 4 hours from after Day 8 up to Day 29
- $\pm 1, 2$ or 3 days from after Day 29 up to the last measurement as indicated in the [Flow Chart](#)

If scheduled in the [Flow Chart](#) at the same time as a meal, blood sampling, vital signs and 12-lead ECG recordings have to be done first. Furthermore, if several measurements including venipuncture are scheduled for the same time, venipuncture should be the last of the measurements due to its inconvenience to the subject and possible influence on physiological parameters.

For planned individual plasma concentration sampling times refer to the [Flow Chart](#). While these nominal times should be adhered to as closely as possible, the actual sampling times will be recorded and used for determination of pharmacokinetic parameter. The same applies to biomarker sampling and pharmacodynamic parameters.

If a subject misses an appointment, it will be rescheduled if possible. The relevance of measurements outside the permitted time windows will be assessed no later than at the Report Planning Meeting.

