6.2.2 Treatment period

Each subject will receive one dose of the respective trial medication (BI 655088 or placebo) at Visit 2.

Trial medication will be administered as IV infusion by the investigating physician or his designee. Details on treatments and procedures of administration are described in [Section 4.1.4](#).

Study participants will be admitted to the trial site in the evening of Day -1 and kept under close medical surveillance for at least 48 h following the start of infusion. The subjects will then be allowed to leave the trial site after formal assessment and confirmation of their fitness by the investigator or designee. On all other study days, the study will be performed in an ambulatory fashion.

For details on time points and procedures for collection of blood samples for PK analysis, refer to [Flow Chart](#) and [Section 5.5.2](#).

The safety measurements performed during the treatment period are specified in [Section 5.2](#) of this protocol and in the [Flow Chart](#). For details on time points for all other trial procedures, refer to the [Flow Chart](#). AEs and concomitant therapy will be assessed continuously from screening until the end of trial examination.

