6.2.3 End of trial period

For AE assessment, laboratory tests, recording of ECG and vital signs, and physical examination during the end of trial period, see [Sections 5.2.2](#) to [5.2.5](#).

Subjects who discontinue before the end of the treatment period should undergo the end of trial visit.

All abnormal values (including laboratory parameters) that are judged clinically relevant by the investigator will be monitored using the appropriate tests until a return to a medically acceptable level is achieved. Adverse events persisting after trial completion must be monitored until they have normalised or have been sufficiently characterised.

The end of the trial as a whole is defined by the 'last regular visit completed by last subject' or 'end date of the last open AE' or 'date of the last follow-up test' or 'date of an AE has been decided as sufficiently followed-up', whichever is latest.

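### After the single infusion, removal under Protocol 3.3.4.1 cannot reduce exposure; it ends the remaining scheduled safety and PK assessments, including the only post-dose oGTT, while the residual effect period is unknown

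*Protocol*

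**What the plan says.** Protocol 3.3.4.1 lists conditions under which a subject has to be removed from the trial, not only from treatment. Criterion 4 reads "An AE or clinically significant laboratory change or abnormality occurred that the investigator judges to warrant discontinuation of treatment"; its examples include unexplained liver enzyme elevations at any time in the trial, so it reaches well past the infusion. Criterion 5 (AST or ALT at least 3 times ULN with total bilirubin at least 2 times ULN, or need for the DILI checklist) and criterion 2 (interfering concomitant drugs) also make removal mandatory. Removal for non-compliance is optional.

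On what follows removal, 3.3.4.1 says "At the time of discontinuation a complete end of trial examination will be performed if possible and the information will be recorded in the CRFs", and 6.2.3 says "Subjects who discontinue before the end of the treatment period should undergo the end of trial visit".

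Four other provisions bear on this:
- 6.2.2: "Each subject will receive one dose of the respective trial medication (BI 655088 or placebo) at Visit 2". The infusion lasts 120 minutes (2.1.2).
- 5.2.2.2: the residual effect period is not known. "Therefore all AEs reported until the end of trial examination will be considered on treatment". After a subject's end of trial, "The investigator does not need to actively monitor the subject for AEs but should only report relevant SAEs and relevant AESIs" that come to notice.
- 5.2.3.1: "An oGTT will be performed on the morning of Day -5 to -1 (baseline) and Day 29". The end-of-trial examination described in 5.2.5.2 contains no oGTT.
- 6.1 gives time windows for "days from after Day 29 up to the last measurement", so the schedule runs beyond Day 29.

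**The concern.** Removal is useful before dosing and during the infusion, which 2.3 notes can be stopped. After that, the criteria work as if treatment were continuing. The subject keeps the full exposure and loses the scheduled observation of it.

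The loss is selective, because subjects with an AE, a laboratory signal or a hepatic alert are the ones removed. In a first-in-human trial these are the dosed subjects whose later course is of most interest. Counting every AE up to the end-of-trial examination as on treatment is the protocol's answer to an unknown residual effect period. Moving that examination forward weakens it.

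Two planned analyses are affected. Section 7.3.3 compares changes in glucose and insulin AUC from baseline between BI 655088 and placebo, and 7.4.1 imputes no safety values. Section 7.3.2 allows PK data to be declared non-evaluable when samples are missing at important phases of the disposition curve.

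**Working it through.** The protocol states no figure on this point (7.6 reports no power calculation), so the check is a reading of the rules followed by the size of one removal.

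**Following one subject.** A subject has received the full infusion and meets criterion 5 on Day 8.
1. 3.3.4.1: removal is mandatory, with an end-of-trial examination at that time if possible.
2. 5.2.2.2: active AE monitoring ends. Events after the end-of-trial examination are classed as post-treatment there and in 7.3.3.
3. 5.2.3.1 with 5.2.5.2: the Day 29 oGTT is not done, and the end-of-trial examination does not replace it.
4. 7.3.3 with 7.4.1: there is no post-dose oGTT value and no imputation, so the subject contributes nothing to that comparison.
5. Still followed: open AEs (5.2.2.2), clinically relevant abnormal values (6.2.3) and the hepatic alert by the DILI checklist (5.2.2.1).

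Scheduled observation lost: 29 − 8 = 21 days, plus the measurements after Day 29.

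**Precision of the oGTT AUC change.** Inputs: 6 active subjects per dose group and 6 × 2 = 12 pooled placebo subjects (3.1; pooling in 7.3.3). Results are 95% CI half-widths in SD units.

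| Quantity | Formula | 6 active | 5 active | Ratio |
|---|---|---|---|---|
| Group mean | t(0.975, n−1)/√n | 2.571/√6 = 1.049 | 2.776/√5 = 1.242 | 1.18 |
| Difference from placebo | t(0.975, n+10) × √(1/n + 1/12) | 1.060 | 1.135 | 1.07 |

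**Late events not otherwise seen.** If no case is observed, the exact two-sided 95% upper limit is 1 − 0.025^(1/n): 45.9% for n = 6 and 52.2% for n = 5.

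**Primary endpoint (subjects with drug-related AEs).** A subject removed for a drug-related AE is already counted, so nothing changes. For a subject removed on other grounds, assume a probability p of 0.10 to 0.25 of a first drug-related AE later; the protocol gives no such figure. The expected under-count is p/6 = 1.7 to 4.2 percentage points in that dose group, or p/36 = 0.3 to 0.7 points among the 6 × 6 = 36 active subjects.

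**How often.** No removal rate is stated. With an assumed per-subject risk of 2%, 5% or 10%, the chance of at least one removal, 1 − (1 − r)^6, is 11%, 26% or 47% in a group of 6 active subjects.

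**The case against.** The strongest reply is that little is lost in practice. Criterion 4 depends on the investigator's judgement and, read literally, can hardly be met once no treatment remains. Subjects with hepatic alerts go to the DILI checklist, known AEs and abnormal values are followed, and relevant SAEs and AESIs that come to notice are still reported. Cmax will normally have been captured, and AUC0-tz runs only to the last quantifiable point, so the PK loss falls mainly on AUC0-∞. Replacement (3.3.5) can restore group size. If the oGTT comparison pooled all active subjects, going from 36 to 35 would widen the half-width only from 0.671 to 0.674 SD, about 0.4%. The Flow Chart is not in the available text and could carry a note on follow-up after removal.

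Much of this stands as a limit on size. The primary count barely moves, the trigger event is followed, and the PK effect is partial. It does not remove the point:
- Criteria 2 and 5 are mandatory whatever the reading of criterion 4, and the liver-enzyme example in criterion 4 shows that use after dosing is intended.
- Following a known event is not surveillance for new ones.
- Replacement supplies another subject's data, not the later data of the subject removed.
- Sections 7.1.1 and 7.3.3 set the dose levels and active groups against pooled placebo, so the per-group figures apply.
- A Flow Chart note keeping removed subjects on schedule would conflict with 3.3.4.1, which places the end-of-trial examination at discontinuation.

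**Conclusion.** The concern holds and should be fixed. For a subject who has completed the infusion, removal under the medical criteria gives no reduction in exposure. It ends scheduled detection of new AEs, late PK sampling and, if it comes before Day 29, the only post-dose oGTT. One such removal costs a sixth of a dose group's post-dose oGTT data, with the CI widening by 18% for the group mean and 7% for the contrast with placebo if the subject is not replaced. The effect on the primary endpoint is nil for removals due to drug-related AEs and small otherwise, under the assumed 10% to 25% risk of a later first event.

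The conclusion rests on the text of 3.3.4.1, 5.2.2.2 and 6.2.3, with the Flow Chart unseen. How often it would matter cannot be stated, because no removal rate is given.

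**What to change.** In 3.3.4.1 and 6.2.3, separate stopping the infusion from withdrawing from the trial:
- A subject who has received any study drug and meets criterion 2, 4 or 5, or does not comply, has any running infusion stopped where indicated. He stays in the scheduled safety, AE, oGTT and PK assessments up to the planned end-of-trial visit.
- Exceptions are withdrawal of consent and inability to attend, including criterion 3. A single assessment may be omitted where it is medically inappropriate.
- PK-relevant violations, such as use of restricted medication, are handled by exclusion from the PK analysis, as 7.3.2 already provides.

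The cost is a change of wording in two sections. No new procedure is needed; a few subjects attend visits that are already planned.
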